5.1 Changes in the Planned Analyses

This SAP is based on protocol versions and amendments described in section 1. Compared to these, the following changes have been implemented in the SAP:

- All model-based analyses will include adjustment for a dichotomous categorization of country as Japan vs other countries.
- A number of additional subgroup analyses were added, as described in section 5.8.
- An additional sensitivity analysis for the primary endpoint was added for handling of subjects who had a WLL (section 5.3.6)
- Number of WLLs over time, was included as a further secondary endpoint in the double-blind period, as described in section 5.3.7.

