5.3.6 Primary Efficacy analysis

The primary efficacy variable, (A-a)DO₂, will be collected at Screening, Baseline (randomisation), Week 4, 12 and 24 during treatment period, and at Week 12, 24, 36 and 48 during the follow-up period. All (A-a)DO₂ values reported in the CRF will be recalculated for statistical analyses using the equation:

$$Aa\ Gradient = \left(F_i O_2 (P_{atm} - P_{H_2O}) - \frac{P_a CO_2}{0.8} \right) - P_a O_2$$

where F_iO₂ is fraction of inspired oxygen

P_{atm} is ambient atmospheric pressure

P_{H₂O} is saturated vapour pressure of water at body temperature (set to 47 mmHg / 6.266 kPa)

P_aCO₂ is arterial partial pressure of carbon dioxide

P_aO₂ is arterial partial pressure of oxygen

Any of these assessments reported in kPa will be converted to a result in mmHg before the calculations, this will be done using a factor k=7.5.

The primary efficacy endpoint, absolute change from baseline of (A-a)DO₂ after 24-weeks treatment, will be analysed based on an ANCOVA model including treatment group, WLL (stratification), Japan vs other countries, and baseline (A-a)DO₂. The data from the three treatment groups will be analysed all together (all treatment groups included in one model). Contrasts will be set up to estimate treatment differences in change from baseline with 95% confidence intervals (CI) and the corresponding p-value for Molgramostim OD vs. Placebo and for Molgramostim intermittently vs. Placebo.

For each analysis two sided tests will be performed where the null hypothesis is that there is no difference between treatment groups, which will be tested against the alternative that

there is a difference. Control for type-1 error inflation due to multiple testing will be handled as described in section 5.4.

A de-facto estimand approach will be applied, where for the primary analysis, all observed data will be included, irrespective of subject adherence to the randomised treatment. Subjects who withdraw from their randomised treatment before week 24 will be followed up through to week 24, and their week 24 data will be considered as primary, irrespective of treatment discontinuation, treatment interruption(s), use of rescue medication (WLL or other), etc.

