- Subjects who withdraw from the study early and who do not have week 24 data available will have their (A-a)DO₂ measurement imputed using multiple imputation (MI). This will be done by first ensuring a monotone missing data pattern by imputation of intermediate missing data (baseline, Week 4 and Week 12) by a Markov chain Monte Carlo (MCMC) approach, where imputations are done by treatment group Japan vs other countries, and WLL (stratification) if possible (strata may be dropped depending on the number of observations per combination). The imputation will be done generating 10 data sets. When monotone missingness has been accomplished, then the remaining missing data, up to and including Week 24, will be imputed using a monotone regression approach using treatment and WLL (stratification) as class variables. Each replication of the data, including the imputed missing values, will then be analysed using the ANCOVA used in the primary analysis, and estimates will be pooled using proc MIANALYZE SAS®. (this approach is valid under assumption that data is missing according to MAR).

- If superiority has been determined for any of the comparisons planned for the primary endpoint, a tipping point analysis (TP) will be applied where subjects with a missing endpoint (Week 24) in the group for which superiority has been determined will be assigned progressively worse (A-a)DO₂. This will be done by generating imputed data according to the previous step and using the MNAR option in proc MI SAS® to adjust imputed Week 24 data with an appropriate sized shift parameter in the superior arm in an iterative manner until the results shift from significant (P<0.05) to non-significant (P>0.05). From this analysis, results will be presented including overall estimates at the tipping point, as well as descriptive statistics for imputed data vs non-imputed data.
- A “reasonably worst case” scenario. For the primary analysis, patients in either of the active arms will have the value of the 10th percentile from their dose arm imputed (i.e. approximately the 3rd worst case) whilst patients in the placebo arm will have the median for the placebo arm imputed. This analysis will be based on the same ANCOVA model as applied for the primary analysis.

The above sensitivity analyses can be considered as de-facto approaches. The following sensitivity analyses will also be conducted as de-jure estimation approaches to evaluating data:

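### The Week 24 imputation step leaves out the Japan term that the analysis model contains, and 10 imputations leave the tipping-point result dependent on the random seed

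*SAP*

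**What the plan says.** The multiple-imputation analysis in SAP 5.3.6 (Sensitivity Analyses) has two steps.

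- An MCMC step fills intermediate gaps at baseline, Week 4 and Week 12, "where imputations are done by treatment group Japan vs other countries, and WLL (stratification) if possible".
- A monotone regression then fills everything still missing up to Week 24, "using treatment and WLL (stratification) as class variables". Japan is not named here.

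On the number of imputations the SAP says "The imputation will be done generating 10 data sets". No seed is given, and no tolerance for Monte Carlo error. Each completed data set "will then be analysed using the ANCOVA used in the primary analysis", that is, an "ANCOVA model including treatment group, WLL (stratification), Japan vs other countries, and baseline" (A-a)DO₂.

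The tipping-point analysis works by "generating imputed data according to the previous step and using the MNAR option in proc MI", increasing the shift in the superior arm "until the results shift from significant (P<0.05) to non-significant (P>0.05". The rescue-treatment analysis in the same section re-imputes in the same way, and SAP 5.3.7 plans a similar imputation analysis for 6MWD and SGRQ.

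Two general rules bear on this. SAP 5.1 states: "All model-based analyses will include adjustment for a dichotomous categorization of country as Japan vs other countries". SAP 5.5 extends the Japan adjustment to all parametric analyses. SAP 5.3.6 also classes all these sensitivity analyses as supportive and outside type I error control.

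**The concern.** An imputation model should normally contain at least the terms of the model that analyses the completed data. Here the step that creates the endpoint value drops a term that both the ANCOVA and the preceding MCMC step carry. The SAP says the approach is valid under missing at random. With Japan left out, that statement does not cover missingness that depends on Japan.

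The second issue is precision. With 10 imputations the pooled estimate and its standard error still depend visibly on the random draws. For most results that is a nuisance. For a tipping point it matters more, because the quantity reported is the shift at which a noisy p-value crosses a fixed line. Two programmers following the SAP exactly could report different tipping points and so different impressions of robustness.

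**Working it through.** **Plan's own figures.** The documents state nothing about imputation precision beyond the 10 data sets. As a check on the inputs, the original sample size (SAP 3.2: difference 10 mmHg, SD 7.5, two-sided alpha 0.01, 90% power, 2:1) reproduces with the noncentral t: 14 + 28 = 42, power 90.8%.

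**Inputs from the documents.** Ten imputations, threshold P = 0.05 and the model terms (SAP 5.3.6); SD 7.5 mmHg and 135 subjects, 45 per arm (SAP 3.2).

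**Assumptions.** Protocol 12.1.5 expects only minimal missing Week 24 data and gives no rate, so 5%, 10% and 20% were used. Also assumed: Japan share 30%, Japan effect on Week 24 change 0 to 10 mmHg, WLL stratum 10%, correlation between visits 0.6^(lag/2), and earlier visits included as predictors in the monotone step.

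**Step 1: seed-to-seed noise in the p-value.** The Monte Carlo SD of the pooled z is about √(FMI/m), where FMI is the fraction of missing information and m the number of imputations. At a true p of 0.050 (z = 1.96), the range is p = 2[1 − Φ(1.96 ± 2 SD)].

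| FMI | SD of z, m = 10 | p range, m = 10 | SD of z, m = 100 | p range, m = 100 |
|---|---|---|---|---|
| 5% | √(0.05/10) = 0.071 | 0.036–0.069 | 0.022 | 0.045–0.055 |
| 10% | √(0.10/10) = 0.100 | 0.031–0.078 | 0.032 | 0.043–0.058 |
| 20% | √(0.20/10) = 0.141 | 0.025–0.094 | 0.045 | 0.040–0.061 |

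A simulation took 6,000 imputations of fixed data sets, split them into batches of 10 or 100, and pooled each batch by Rubin's rules. It agrees: with about 10% missing, the 95% range of p was about 0.032–0.082 at m = 10 and 0.044–0.057 at m = 100.

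**Step 2: seed-to-seed noise in the tipping shift** (same simulation; one simulated trial per row; mmHg).

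| Missing | MI p | Shift from all 6,000 | 95% range, m = 10 | 95% range, m = 100 |
|---|---|---|---|---|
| 5% | 0.023 | 9.59 | 4.06–14.33 | 8.07–10.87 |
| 10% | 0.020 | 5.79 | 2.22–8.64 | 4.81–6.56 |
| 20% | 0.019 | 2.81 | 0.74–4.80 | 2.07–3.34 |
| 10% | 0.00002 | 30.39 | 27.66–32.63 | 29.70–31.05 |

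Over all simulated trials the SD of the shift fell from 1.1–2.7 mmHg at m = 10 to 0.3–0.8 mmHg at m = 100.

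**Step 3: leaving out Japan.** There were 1,000 simulated trials per scenario with m = 10 and no true treatment effect. Bias is in the once-daily versus placebo contrast; its standard error is about 1.5 to 1.6 mmHg.

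| Scenario | Bias without / with Japan (mmHg) | Rejection without / with Japan |
|---|---|---|
| 10% missing, unrelated to Japan, effect 5 mmHg | 0.008 / 0.006 | 0.055 / 0.058 |
| 20% missing, unrelated to Japan, effect 5 mmHg | 0.055 / 0.075 | 0.052 / 0.050 |
| 10% missing, dropout by Japan opposite across arms, effect 5 mmHg | −0.160 / 0.023 | 0.035 / 0.037 |
| 20% missing, same pattern, effect 5 mmHg | −0.366 / 0.025 | 0.068 / 0.055 |
| 10% missing, extreme pattern, effect 10 mmHg | −0.707 / 0.037 | 0.070 / 0.055 |

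In the extreme pattern all once-daily dropout is in Japan and none of the placebo dropout is. When missingness is unrelated to Japan, the omission mainly shrinks the Japan coefficient itself (5.01 to 4.64 at 10% missing), not the treatment contrast.

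**The case against.** The case on the other side is substantial.

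- **Invalid p-values.** A reader might infer that the MI and tipping-point p-values are mis-specified in a way that matters. The documents do not support that. Randomisation should roughly balance Japan across arms, earlier visits carry part of its effect, and Step 3 shows near-nominal behaviour unless dropout depends on Japan in opposite directions by arm. Nothing in the documents suggests such a pattern. This stands.
- **Drafting slip.** SAP 5.1 and 5.5 could be read as already requiring Japan in the imputation regression. That is plausible, but the sentence that specifies the step lists its class variables and omits Japan, so the text still needs correcting.
- **Cross-check.** The MMRM in SAP 5.3.6 assumes missing at random, includes Japan and needs no imputation; SAP 5.3.7 plans it for 6MWD and SGRQ too. This stands for the MI result. It does not replace the tipping point.
- **Only one analysis searches for a threshold.** The MI analysis simply reports an estimate and p-value. This stands.
- **No confirmatory decision depends on it.** The analyses are supportive, and the tipping point runs only after superiority is shown. On the plan's own figures z would be 10 / (7.5 × √(2/45)) = 6.3, where a Monte Carlo SD of 0.1 is immaterial. This stands and limits the weight of the point.
- **One hundred is not a magic number.** At 10% missing information the range is still 0.043–0.058. True: more imputations reduce the noise, and only a stated seed makes the run exactly repeatable. The fix needs both.

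Protocol 12.1.5 presents multiple imputation as the handling for missing Week 24 data, while the SAP lists it as a sensitivity analysis. That is a separate question and is not used here to add weight.

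**Conclusion.** The point holds as a free improvement. The Week 24 imputation model is narrower than the analysis model it feeds, and it is inconsistent with SAP 5.1, 5.5 and the MCMC step beside it. The practical effect on the treatment contrast is small: no visible bias when missingness is unrelated to Japan, and 0.16 to 0.37 mmHg with differential dropout and a 5 mmHg Japan effect.

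The main consequence is noise. With 10 imputations, a pooled p-value near 0.05 can fall on either side of it by seed alone. When the primary result is significant but not overwhelming (p about 0.02), the tipping shift can span about 4 to 10 mmHg from one seed to another, against the 10 mmHg difference the trial was first sized on. With a very strong result the shift stays far from zero and the conclusion does not change.

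These sizes rest on the assumed missing rate, Japan share, Japan effect and visit correlation. None of them is in the documents.

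**What to change.** Before unblinding, amend SAP 5.3.6 in three places.

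1. Add Japan versus other countries to the class variables of the monotone regression step, and name baseline and the earlier visits as its predictors.
2. Raise the number of imputations from 10 to at least 100 for the MI, rescue re-imputation and tipping-point analyses, and for the 6MWD and SGRQ imputation analyses in SAP 5.3.7.
3. State the random seed in advance.

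The change amounts to a few program settings and a sentence or two of text. The only cost is run time; no data collection, sample size or confirmatory test is affected.

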5.3 Hypotheses and Statistical Methods

5.3.1 General

For all efficacy analyses, primary and secondary, where statistical tests are conducted (see separate sections below) the null hypothesis is that there is no treatment difference, which

will be tested against the alternative hypothesis, that there is a treatment difference. All tests will be two-sided.

In general, all summary statistics will be presented for all treatment groups.

In this trial, for subjects withdrawing from treatment early, attempts will be made to continue follow-up and collect the planned data, as described in protocol. If a subject is withdrawn from the trial early, the investigator should attempt to complete all required trial assessments (such as those at Week 24 if withdrawn during the Double-blind treatment period). Assessments for subjects withdrawing from trial early, and where any measurements related to endpoints to be statistically analysed are collected on the Week 24 Visit in the eCRF, (i.e. if intermittent visits are missing), then these assessments will be reallocated to the visits closest in time to the time point of withdrawal. This is done in order to avoid an unintended partial LOCF approach to analysis of data.

For statistical analyses of the primary and key secondary efficacy endpoints, the type-1 error rate will be controlled, as described in section 5.4. In addition a number of sensitivity analyses will be conducted, as described in the following sections. An overview of the planned statistical analyses and how inflation of alpha, due to multiple testing, will be prevented can be seen in figure 2.

Results applicable to the follow-up period will be summarised both according to randomised treatment arms under the double-blind treatment period and in total.

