5.4 Level of Significance, Multiple Comparisons and Multiplicity

For all significance tests, exact p-values (to four decimal places) will be calculated and quoted.

[figure not shown]
There are two dose regimens and one primary efficacy parameter, and three key secondary efficacy parameters, which are intended to support conclusions based on the primary parameter. For these analyses type-1 error rate will be controlled as described below. In addition, sensitivity analyses and several other endpoints will be considered as supportive and descriptive, and no adjustments for multiplicity will be made for these analyses.

Two sets of comparisons (for the primary and key secondary endpoints) will be carried out. The first will be of once daily dosing vs. placebo, and the second will be of intermittent dosing vs. placebo. In order to account for multiplicity, an overall hierarchical testing procedure will be applied in the steps between primary and secondary endpoints, while a Hochberg procedure will be applied among the secondary endpoints. An overall significance level of 0.05 will be applied.

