The first step will be the test of once daily dosing vs. placebo for the primary endpoint. If the null hypothesis is rejected, then once daily dosing vs. placebo will be tested for the three key secondary endpoints using a Truncated Hochberg procedure (applying a truncation factor of 0.75). If at least one null hypothesis is rejected among the key secondary endpoints, then the hierarchical testing will proceed with comparing intermittent dosing vs. placebo for the primary endpoint based on a significance level depending on the number of successes in previous step, as applicable to the truncation factor used. Last, if the null hypothesis is rejected for the comparison of primary endpoint in intermittent dosing vs placebo, then the key secondary endpoints will be compared for intermittent dosing vs placebo using the regular Hochberg and based on an overall significance level corresponding to the previous step. The truncated Hochberg procedure using a truncation factor of 0.75 among the tests in the family of secondary tests between Molgramostim OD and Placebo, implies ordered alpha levels of 0.0417, 0.0229, 0.0167, while preserving alpha 0.05 for the first test between Molgramostim Int. and Placebo if all null hypotheses are rejected, and 0.0083 and 0.0042 if only two or one of the ordered hypotheses are rejected, respectively. The steps of the testing procedure applied to account for multiple testing among the primary and key secondary endpoints are illustrated in figure 2.

All of the analyses will be tabulated separately (irrespective of statistical significance), although an overview of the results of the steps in the testing procedure will be also tabulated.

Figure 2 Overview of Analyses for Primary and Key secondary endpoints

Results from analyses denoted “Main analysis” will be part of testing procedures where adjustments to control for multiple testing will be implemented.

MI – Multiple imputation,

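### The tipping-point search stops at P = 0.05 even when intermittent dosing was declared superior at 0.0083 or 0.0042, so it overstates how robust that claim is to missing data

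*SAP*

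**What the plan says.** The tipping-point bullet in SAP 5.3.6 is conditional on a positive result: "If superiority has been determined for any of the comparisons planned for the primary endpoint, a tipping point analysis (TP) will be applied". Missing Week 24 values are first multiply imputed. The procedure will then "adjust imputed Week 24 data with an appropriate sized shift parameter in the superior arm", in steps, "until the results shift from significant (P<0.05) to non-significant (P>0.05"). No other stopping level is given, and the rule is the same for both regimens.

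SAP 5.4 sets the level at which each primary comparison is tested. Once-daily dosing versus placebo comes first, at 0.05. If it succeeds, once-daily dosing is tested on the "three key secondary endpoints using a Truncated Hochberg procedure (applying a truncation factor of 0.75"). Intermittent dosing versus placebo on the primary endpoint is reached if at least one of those three is rejected, and is then tested "based on a significance level depending on the number of successes in previous step, as applicable to the truncation factor used". The carried level is 0.05 when all three are rejected, "and 0.0083 and 0.0042 if only two or one of the ordered hypotheses are rejected".

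SAP 5.3.6 also says that the sensitivity analyses are supportive and outside the type-1 error procedure. It gives their purpose as judging how robust the results are to missing data.

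**The concern.** A tipping-point analysis should find how unfavourable the missing values must be before a declared result no longer stands. For intermittent dosing the declared result may rest on 0.0083 or 0.0042. A search that ends at 0.05 then carries on after the superiority claim has already failed, and reports a larger shift than the one that overturned it. A reader would take the second regimen's result to be more resistant to missing data than it is.

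The branch is a realistic one. The 0.05 level needs all three once-daily key secondaries, including time to WLL. SAP Appendix 2 records 4 WLL events among 78 randomised subjects. It calculates 47 subjects for 80% power and 63 for 90%, assuming event rates of 5% and 20%, and calls these sizes probably too optimistic. The target is 45 per arm. If the intermittent test is reached at all, a reduced level is a serious prospect.

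The mismatch comes from the SAP's own gate. Under protocol 12.1.3 all key secondaries must be significant before intermittent dosing is tested, so its level would always be 0.05.

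**Working it through.** **Step 1: reproduce the levels in SAP 5.4.** Inputs: overall α = 0.05 ("An overall significance level of 0.05 will be applied"), truncation factor γ = 0.75 and m = 3 tests.

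Critical values are [γ/k + (1 − γ)/m] × α:
- k = 1: (0.75 + 0.0833) × 0.05 = 0.0417
- k = 2: (0.375 + 0.0833) × 0.05 = 0.0229
- k = 3: (0.25 + 0.0833) × 0.05 = 0.0167

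With A hypotheses not rejected (A = 1 or 2), the carried level is α − [γ + (1 − γ)A/m] × α:
- A = 0: the full 0.05
- A = 1 (two rejected): 0.05 − 0.8333 × 0.05 = 0.0083
- A = 2 (one rejected): 0.05 − 0.9167 × 0.05 = 0.0042

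All six figures agree with the SAP.

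**Step 2: convert to critical values.** "All tests will be two-sided" (SAP 5.3.1). Under a normal approximation, with the carried levels unrounded (0.05/6 and 0.05/12):
- 0.05: |z| = 1.960
- 0.0083: |z| = 2.638, which is 0.678 above 1.960
- 0.0042: |z| = 2.865, which is 0.905 above 1.960

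**Step 3: the excess on the scale of the mean difference.** Inputs: SD 7.5 mmHg (SAP 3.2, Table 1) and 45 per arm (SAP 3.2).

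SE = 7.5 × √(2/45) = 1.58 mmHg.

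- At 0.0083: 0.678 × 1.58 = 1.07 mmHg
- At 0.0042: 0.905 × 1.58 = 1.43 mmHg

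**Step 4: the excess in the shift parameter.** If a fraction f of the superior arm is missing at Week 24, shifting those values by d moves the arm mean by f × d. The excess in d is therefore the excess in the mean divided by f. Neither document gives f, so 5% to 20% is an assumption. Column A keeps the SE at 45 per arm. Column B uses the observed cases only, assuming the same f in both arms: SE = 7.5 × √(2/(45(1 − f))).

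| Missing f | A: 0.0083 / 0.0042 (mmHg) | SE for B | B: 0.0083 / 0.0042 (mmHg) |
|---|---|---|---|
| 5% | 21.4 / 28.6 | 1.622 | 22.0 / 29.4 |
| 10% | 10.7 / 14.3 | 1.667 | 11.3 / 15.1 |
| 15% | 7.2 / 9.5 | 1.715 | 7.8 / 10.4 |
| 20% | 5.4 / 7.2 | 1.768 | 6.0 / 8.0 |

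**Step 5: an example.** Take f = 10%, SE = 1.667 and an unshifted P of 0.004 (|z| = 2.878). The shift needed is (2.878 − critical z) × 1.667/0.10:
- to cross 0.05: 15.3 mmHg
- to cross 0.0083: 4.0 mmHg
- to cross 0.0042: 0.2 mmHg

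The plan would report 15.3 mmHg. A claim made at 0.0083 is lost at 4.0 mmHg, and one made at 0.0042 at 0.2 mmHg.

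There is also an extreme case. Superiority is declared on the main ANCOVA, while the search starts from the multiply imputed data. If imputation alone gave a P between 0.0083 and 0.05, the claim would fail with no shift at all, and the plan would still report a positive tipping shift.

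**The case against.** The best counter-argument is that this is a supportive analysis. SAP 5.3.6 and 5.4 both place the sensitivity analyses outside multiplicity control, and 95% confidence intervals are reported for both contrasts whatever level is carried. A nominal 0.05 stop fits that convention and gives one yardstick for both regimens. With a level-dependent stop, identical intermittent (A-a)DO₂ data would give different tipping shifts according to how many once-daily secondaries succeeded. Protocol 12.1.5 is looser still: its tipping point is where the result turns to favour placebo. The trigger is also narrow. It needs once-daily success on the primary, exactly one or two secondaries rejected, intermittent success at the reduced level, and missing Week 24 data in that arm.

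Some of this stands. No confirmatory conclusion can change, and comparability between regimens is a good reason to keep the 0.05 crossing as an extra output. The per-subject figures should not be read against the planning difference of 10 mmHg, which is a between-arm mean difference. On that scale the excess is 1.07 or 1.43 mmHg, or 11% to 14% of 10 mmHg. Protocol 12.1.5 expects very little missing data, and with few missing subjects the tipping shift may be implausibly large at any threshold.

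What does not stand is that the supportive label makes 0.05 the right stop. The label means that no α is spent. The analysis is still triggered by a superiority declaration, and SAP 5.3.6 refers type-1 error control for this endpoint to 5.4. The point at which that declaration fails is set by the level in 5.4. The search would pass the stricter crossing on its way to 0.05, but the SAP does not commit to reporting it.

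**Conclusion.** The concern holds. When intermittent dosing is declared superior at 0.0083 or 0.0042, the planned search always reports a larger shift than the one that loses the claim. The direction is certain, because 0.05 is the looser threshold.

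The size is illustrative. It is 1.07 or 1.43 mmHg in the mean difference, and roughly 5 to 29 mmHg per missing subject over 5% to 20% missing. These figures rest on the planning SD of 7.5 mmHg (from a previous trial's before- and after-treatment values, not the ANCOVA residual), 45 per arm, a normal approximation, and an assumed missing fraction. They make no allowance for between-imputation variance or for the residual variance growing as values are shifted.

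The 0.05 stop is correct for once-daily dosing and for intermittent dosing after three rejections. The primary analysis is unaffected, so this is a minor correction worth making.

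**What to change.** In the tipping-point bullet of SAP 5.3.6, replace the fixed 0.05 stop with the significance level at which that comparison was declared superior under 5.4: 0.05, 0.0083 or 0.0042 as applicable. If a common yardstick for the two regimens is wanted, report the 0.05 crossing as well, labelled nominal.

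The cost is one clause. It needs no new data, no change to the imputation model and no change to the primary analysis, and both crossings come from the same iterative run.
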